5.2 Restaging Following mFOLFIRINOX

After induction chemotherapy (up to 4 cycles), patients will have a CT scan for re-staging. Re-staging scans should be scheduled within 2 weeks following completion of induction mFOLFIRINOX. To allow for scheduling complications, outside sites may perform the simulation (SIM) scan during the final cycle of chemotherapy up to 4 weeks prior to start of treatment. If the subjects are randomized to the SBRT arm and the SIM was more than 4 weeks prior to treatment start date, a re-SIM will be performed to ensure that the plan is still appropriate for tumor treatment.

- If there is radiological or clinical evidence of disease progression, patient will not continue with the randomized portion of this study, but should be treated according to treating physician's discretion. (Based upon the study by Conroy *et al*, the progression-free survival at 3 months is estimated to be 75%; therefore the number of patients evaluated for the protocol and ultimately enrolled will be adjusted accordingly.) These patients will continue to be followed as part of the study.
- If a patient has radiologically responding or stable disease, s/he may proceed with randomization as described in the following section. Patients may undergo surgical resection at any time if clinically appropriate after surgical evaluation.

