5.3 Randomization to +/- SBRT

Participating centers will submit re-staging scan reports (and images as requested) within 5 business days of the scan's final report date to Stanford, along with documentation of consent. These should be sent in a secure electronic mail message or fax to the PI ([name]) and Clinical Research Coordinator [name] with subject line: "SECURE: STUDY PATIENT FOR RANDOMIZATION". Stanford research staff will randomize the subject by participating site and within the next business day, will send an electronic message to the PI and Research Coordinator from the participating center with the outcome and instructed treatment plan.

Randomization will be done with R software, a randomized block design. It will be performed by a Stanford Statistician or the Stanford study coordinator who will maintain a password-protected list and assign patients to the treatment arms as each patient is enrolled at each institution. Randomization Arm will be confirmed by two coordinators prior to electronic notification and written documentation (Note to File) of the treating physician and outside research coordinators.

Subjects **randomized to SBRT** are allowed up to an 8-week break between induction chemotherapy and radiation treatments.

Subjects **randomized to mFOLFIRINOX** can continue directly with that treatment. Any breaks between mFOLFIRINOX cycles will be determined by the treating Medical Oncologist and are permitted for up to 8 weeks.

If a subject exceeds the allowable 8-week break between treatments, s/he may continue treatment “off protocol” and as recommended by the treating Medical Oncologist or according to local standard of care. These subjects will be followed for overall survival and progression-free survival. Subsequent data analysis will be performed on an intention-to-treat basis.

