6.2 SBRT Treatment Delivery

All patients will receive 5 fractions of 8 Gy allowing up to 30% dose heterogeneity, delivered over a five-day period (ideally all 5 fractions should be delivered Monday through Friday however the 5 fractions may be delivered over 2 weeks as long as the patient receives at least 2 fractions per week). SBRT treatment planning and delivery must be completed at a participating site. The recommended interval between induction chemotherapy followed by SBRT and between SBRT followed by chemotherapy is 2-4 weeks. However, it is acceptable to administer SBRT and chemotherapy within 8 weeks of each other.

If a patient is unable to adhere to the protocol schedule for SBRT treatment, the patient will continue treatment off protocol and as recommended by the treating Medical Oncologist or according to local standard of care. These patients will be followed for overall survival. Subsequent data analysis will be performed on an intention-to-treat basis.

All patients must start SBRT within 4 weeks of the simulation scan and may have up to an 8-week break between radiation and chemotherapy.

For LINAC-based, treatment should entail:

- 1) Initial patient positioning based on either kV or volumetric kV (cone-beam CT) imaging with shifts to bony anatomy as appropriate.
- 2) Orthogonal kV/MV or kV/kV projection imaging to verify the location of the fiducials prior to delivery of first treatment beam. A secondary shift based on the location of fiducials may be utilized, as indicated by the position of the fiducials. For free-breathing treatments, kV fluoroscopic images should be obtained to confirm the anticipated position of these fiducials during the entire respiratory cycle.
- 3) Active monitoring of treatment delivery accuracy using kV and/or MV projection imaging, either immediately before or during all (or a subset of) treatment fields.
- 4) Patient-specific dosimetric QA performed as per standard practice at each participating institution.

For SBRT, treatment should entail:

- 1) Initial orthogonal images obtained to confirm location of fiducial seeds.

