7.1 Chemotherapy following SBRT

For patients randomized to SBRT, mFOLFIRINOX should resume within 8 weeks following completion of SBRT. If this schedule cannot be met, the subject may continue treatment "off protocol" and as recommended by the treating Medical Oncologist or according to local standard of care. These patients will be followed for overall survival and progression-free survival. Subsequent data analysis will be performed on an intention-to-treat basis.

Dosing and modification guidelines for mFOLFIRINOX are provided in Section 9, **however, chemotherapy schedule modifications and dose reductions are allowed and are left to the discretion and clinical judgment of the treating medical oncologist.** A total of at least 6 cycles of mFOLFIRINOX is recommended but the total number of cycles

is left to the clinical judgement of the treating oncologist. As standard practices are changing and Leucovorin is not widely used, we will allow the omission of this drug during both induction and treatment phases of the study.

Participating centers at all times should follow the Study Calendar (Section 14) and ensure that all records and study materials are collected and reported properly.

Since mFOLFIRINOX is an accepted standard of care, chemotherapy may be administered in a community setting as long as the treating oncologist assumes responsibility for the follow up care and reporting requirements. It is recommended that the patient be evaluated at a participating site every 3-6 months.

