14. STUDY CALENDAR

Activity	Induction Chemotherapy				Study Treatment	Follow-up (Time From Completion of Study Treatment) ^j							
	Screening	Study Enrollment	Induction Chemo / mFFX ^g	Re-staging ^c		SBRT ^d	mFFX 2 cycles ^f	4-8 wks ^k	3 ^j mos	6 ^j mos	9 ^j mos	12 ^j mos	Yr 2-Q 6 ^j mos
Biopsy	X				R								
Negative Pregnancy test ^a	X				A								
Consultation	X	X	X ^g		N			X ^k	X	X	X	X	X
ECOG PS	X	X			D			X ^k	X	X	X	X	X
Labs: CBCD, CMP, CA19-9 (CEA optional)	X	X ^b	X ^g		O		X ^h	X ^k	X	X	X	X	X
Study/research labs ⁱ (optional)		X ⁱ			M		X ⁱ	X ^k	X ⁱ	X ⁱ	X ⁱ	X ⁱ	X ⁱ
Eligibility		X			I								
Informed Consent		X			Z								
Study Registration		X			E								
QOL		X						X ^k	X	X	X	X	X
Scan: CT or MR	X			X ^c				X ^k	X	X	X	X	X
PET/CT ^e	X ^e								X ^e				
AE evaluation						X	X ^h	X ^k	X	X	X	X	X
Seed placement						X							
Meds: PPI and pain meds ^j								X ^k	X	X	X	X	X
Sim/setup scans						X							
SBRT						X ^d							
Maintenance mFOLFIRINOX ^{fh}								X-----X ^{fh}					

^a Pregnancy test by urine or serum, for women who are not post-menopausal as defined in Appendix III.

^b Labs should be done within 30 days of eligibility confirmation.

^c Re-staging scan should be done within 2 weeks following completion of induction mFOLFIRINOX cycles.

^d SBRT should begin within 4 weeks of simulation and 8 weeks of the last chemotherapy; dose is 40 Gy (8Gy in 5 fractions).

^e PET-CTs are recommended but not required; if only 1 follow-up PET-CT is possible, recommendation is at 3 months.

^f mFOLFIRINOX should resume within 8 weeks after study treatment, and any breaks between chemotherapy cycles should not exceed 8 weeks. Patients may continue on maintenance mFFX as tolerated or per clinical judgment of treating physician.

^g Induction chemo/mFFX prior to enrollment is allowed through the 4th cycle of mFFX. No more than 4 cycles are allowed prior to randomization. The re-staging scan could be done within 2 weeks of completion of the chemotherapy cycle; records from labs and clinic visits are not required; mFFX infusion records should be collected.

^h Labs during mFFX cycles are as per institutional standard or treating Medical Oncologist. AEs should be assessed with each cycle of mFFX.

ⁱ Study labs are optional and for research purposes as explained in Section 12. Correlative/Special Studies; and may be drawn if patient agrees to this in the consent form.

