17.2 Analysis Populations

Efficacy analysis will be conducted on the intent-to-treat population which includes all randomized patients and on the per-protocol population. The per-protocol population will include patients who have completed 6 or more cycles of mFolfinirox treatment +/- SBRT.

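### The per-protocol PFS comparison selects on completing cycle 6 after randomization, a milestone that comes later with SBRT; the likely bias is small, but the set should be labelled supportive and analysed with delayed entry

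*Combined protocol and SAP*

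**What the plan says.** Section 17.2 names two efficacy populations, intention-to-treat (ITT) and per-protocol, and does not rank them. The second is defined by a completed amount of chemotherapy: "The per-protocol population will include patients who have completed 6 or more cycles of mFolfinirox treatment +/- SBRT". It does not say whether induction cycles count toward the 6.

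Sections 15.1.5 and 17.3.2 start PFS at randomization. A footnote to the Study Calendar (section 14) says "No more than 4 cycles are allowed prior to randomization". Section 7.1 says "A total of at least 6 cycles of mFOLFIRINOX is recommended" and leaves the number to the treating oncologist.

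The arms have different schedules after randomization. Under 5.3 control patients may go straight on with chemotherapy, although "Any breaks between mFOLFIRINOX cycles will be determined by the treating Medical Oncologist and are permitted for up to 8 weeks". For the SBRT arm, 6.2 says "The recommended interval between induction chemotherapy followed by SBRT and between SBRT followed by chemotherapy is 2-4 weeks", with SBRT ideally given over five days. Before randomization, 5.2 says "Re-staging scans should be scheduled within 2 weeks following completion of induction mFOLFIRINOX", and 5.3 then requires the report to be submitted and the arm assigned.

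Under 7.5, on-study chemotherapy continues until a removal criterion is met. Progression is one such criterion, and surgery after a patient becomes resectable is another. Section 17.4 gives no landmark or delayed-entry method for the per-protocol set.

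**The concern.** Membership of the per-protocol set depends on something that happens after the PFS clock starts. A patient who progresses or dies early tends to stop chemotherapy before cycle 6 and drop out of the set. Those who remain still have the weeks before cycle 6 counted as PFS. This is immortal time. If it were equal in the two arms the comparison would stay roughly fair, but the SBRT course and its gaps push cycle 6 later in that arm, so more early events can be removed there.

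At stake is a per-protocol hazard ratio reported beside the ITT result with nothing in 17.2 to mark it as lesser evidence. No decision in the plan rests on it.

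**Working it through.** **Reproducing the design.** Inputs from 17.3.2: medians 6 and 10.2 months, 86 per arm, 60 months of accrual, analysis at 72 months, two-sided 5%. With λ = ln 2 / median, expected events per arm are 86 × [1 − (e^(−12λ) − e^(−72λ)) / (60λ)].

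- Control, λ = 0.1155: 86 × (1 − 0.2498/6.931) = 82.9.
- SBRT, λ = 0.0680: 86 × (1 − 0.4349/4.077) = 76.8.
- Total 159.7, against 160 (83 + 77) in 17.5.2.
- Schoenfeld power with 160 events: Φ(√160/2 × |ln(6/10.2)| − 1.96) = Φ(1.40) = 91.9%, against the stated 91%.

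**When cycle 6 is completed, in weeks from randomization.** This assumes that induction cycles count (section 7.1 speaks of a total, and the calendar shows two cycles after randomization) and that about 2 weeks pass between the end of induction and randomization.

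- Control without breaks: 2 cycles × 2 weeks = 4.
- SBRT: (2 to 4) − 2 = 0 to 2 weeks of waiting left, + 1 week of SBRT, + 2 to 4 weeks' gap, + 4 weeks for two cycles = 7 to 11.
- Lag between arms: 3 to 7 weeks.

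**Events before the milestone.** With a 6-month median and 4.348 weeks per month, the share event-free is e^(−0.1155 × weeks/4.348): 90% at 4 weeks, 83% at 7 and 75% at 11. About 10% of control patients and 17 to 25% of SBRT patients would have an event before their milestone.

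**Effect on the comparison when there is no treatment effect.** Both medians are 6 months, with 86 per arm and the accrual above. An event before the milestone excludes the patient with the stated probability, and PFS is counted from randomization. There were 10,000 replicates (standard error about 0.16 points at 2.5%). Cells show the hazard ratio and the percentage of tests significantly favouring SBRT.

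| Share of early events that exclude | 4 v 7 weeks | 4 v 9 weeks | 4 v 11 weeks |
|---|---|---|---|
| 10% | 0.996, 2.6% | 0.989, 2.9% | 0.987, 2.9% |
| 25% | 0.984, 3.1% | 0.973, 4.0% | 0.965, 3.9% |
| 50% | 0.964, 4.0% | 0.943, 5.8% | 0.924, 7.0% |
| 100% (ceiling) | 0.918, 7.5% | 0.873, 12.6% | 0.829, 19.1% |

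ITT under the same null gives 1.000 and 2.6%.

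**Which rows the documents support.** The calendar times its visits as "Follow-up (Time From Completion of Study Treatment", and study treatment appears to include SBRT and two chemotherapy cycles. The first required scan is at 3 months, with a 1-month window; the earlier visit is optional. If induction counts, cycle 6 ends study treatment, so no required scan precedes it. If induction does not count, cycle 6 comes four cycles, or 8 weeks, after that point, and the earliest required scan comes at 2 months, or 8.7 weeks. There is again none before cycle 6. Early exclusion then rests on death, clinical progression (allowed by 7.4) or unscheduled imaging, so the low-share rows fit best.

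**If induction does not count.** The lag is unchanged (12 v 15 to 19 weeks). At shares of 25 to 50% the hazard ratio is 0.99 to 0.94, with 3.2 to 5.7% favouring SBRT.

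**What can change the direction.**

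- Control milestone spread over 4 to 12 weeks (breaks of 0 to 8 weeks) against SBRT at 7 to 11: 0.993 at a 25% share and 0.97 even at the ceiling.
- Control at 12 weeks against SBRT at 7: 1.02 at 25%, 1.05 at 50%, 1.15 at the ceiling.
- Resection before cycle 6 of 5% of control and 15% of SBRT patients, all from the longer-PFS half (an assumption), 4 v 11 weeks: 1.06 at 25% and 1.01 at 50%. With the arms swapped: 0.87 and 0.84.

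**Delayed entry.** Starting risk time at cycle-6 completion gives null hazard ratios of 0.998 (4 v 7) and 1.001 (4 v 11), with 2.5 to 2.6% favouring SBRT.

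**The case against.** The strongest reply is that the bias needs early events that the calendar mostly will not detect. Patients have just been restaged as stable or better, eligibility requires a life expectancy over 6 months, and no required scan falls before cycle 6. At a 10% share the effect cannot be told apart from the ITT null. This stands, and it sets the size of the point. It does not take the share to zero, because deaths count and progression may be called clinically.

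The second reply is that the direction is not fixed. This also stands: breaks in control and unequal resection can cancel or reverse the lean.

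The third is that the plan already relies on ITT. Sections 5.3, 6.2 and 7.1 each say "Subsequent data analysis will be performed on an intention-to-treat basis" for patients who leave the schedule, and the power and expected events are for all 172 randomized patients. That protects the main result, but it does not tell the reader of 17.2 how to weigh the per-protocol result.

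The fourth is that delayed entry is no cure. It drops a patient who completed 6 cycles but progressed before doing so, and it leaves selection on adherence. In the resection example the delayed-entry null hazard ratio is 1.09 (0.92 with the arms swapped), so in one case it is further from 1 than the uncorrected figure. This stands, and is why the set should be supportive even after correction.

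A reader might infer that the per-protocol analysis gives SBRT a false-positive rate of 19% or more. That needs every early event to exclude the patient. The 27% reached with a 9-week lag also needs randomization on the day induction ends, although restaging and assignment come first. The documents do not support either. A reader might also infer that the trial's main conclusion is compromised; nothing in the plan bases a decision on this set.

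**Conclusion.** The definition in 17.2 builds guaranteed event-free time into the per-protocol PFS comparison, and on the recommended schedule there is more of it in the SBRT arm by about 3 to 7 weeks. The comparison can therefore be biased, toward SBRT on that schedule. The likely size is small: a null hazard ratio of about 1.00 to 0.97, and about 2.5 to 4% false positives favouring SBRT, if 10 to 25% of early events exclude a patient. The 50% row (0.96 to 0.92) and the ceiling (0.92 to 0.83) are upper illustrations only.

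These figures rest on exponential PFS with a 6-month median, about 2 weeks from the end of induction to randomization, no control breaks, and an assumed exclusion share that the documents do not give. ITT, the stated power and the interim rule do not use this set and are unaffected. The point is worth correcting because an unranked efficacy population should not carry a known bias, however modest.

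**What to change.** Change the wording of 17.2 in two respects.

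1. Name ITT as the primary efficacy population, as 5.3, 6.2 and 7.1 imply, and label per-protocol supportive.
2. For per-protocol time-to-event analyses, enter each patient into the risk set at the date cycle 6 was completed (left truncation), so that earlier time and events do not count. State whether induction cycles count toward the 6.

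A common landmark for all event-free patients may be added as a sensitivity analysis. It has no adherence criterion, so it does not replace the per-protocol set.

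No new data are needed: 9.1 already sends administration dates to REDCap, and the calendar asks for induction infusion records. The statistical cost falls on the supportive analysis only. At the design effect it would have about 142 to 137 events and about 82 to 87% power, against 160 events and 91% for ITT. Selection on adherence and resection remains, so the result must not be read as confirmatory. The wording should be settled before any unblinded comparison, so that the choice cannot look driven by the data.

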17.3 Sample Size

17.3.1 Accrual estimates

The study accrual goal is 172 randomized subjects over 60 months among all participating institutions (i.e. 2-3 patients per month). Due to varying eligible patient populations, enrollment may differ at participating centers.

Stanford accrual goal is 6-12 randomized patients annually.

17.3.2 Sample Size Justification

Progression free survival is defined as the time from randomization until progression or death. Individuals who are lost to follow-up prior to death or progression will be censored at the date of last progression evaluation. Based upon previous research, the median progression free survival for individuals treated with mFolfinirox alone is estimated to be 6 months. A sample size of 172 randomized participants (86 per arm) has 91% power to detect an increase to 10.2 months for individuals treated with mFolfinirox plus SBRT as compared to 6 months for those receiving mFolfinirox alone assuming that the data follows an exponential distribution as well as a 60 months of accrual and a minimum of 12 months of follow-up after randomization in a 2-sided test with a type 1 error rate of 0.05.

17.3.3 Criteria for Future Studies

We anticipate that fractionated SBRT with IGRT based linac systems will result in similar progression free survival at one year (80-90%) to single fraction SBRT but with a (20%) decrease in late gastrointestinal toxicity at one year. The current patient population will serve as a comparator for the future trials in terms of time to progression and provide additional information with regards to radiation treatment planning.

17.4 Plan of Analysis

Demographic and clinical characteristics of patients and the characteristics of treated lesions (volume, location, and modality) will be summarized by means, medians, standard deviations, ranges and proportions as applicable.

Time to event outcomes (overall survival, metastasis free survival, and progression free survival) will be summarized using Kaplan-Meier curves and medians with 95% confidence intervals calculated using Greenwood's formula. Cox proportional hazards models will be used to compare treatment groups and to assess risk factors (e.g. biologic markers and PET volume). The effect of site will be tested in the Cox models; the effect of whether or not the patients received Leucovorin will also be tested in the Cox models. The level of response (and other categorical outcomes) will be tabulated at each follow-up interval. Logistic regression and Cox models will be used to assess the proportion with a response category depending upon the level of censoring prior to the annual visit.

The measurements of the volume of the pancreatic tumors based upon CT and PET-CT scans will be compared using paired t-tests or Wilcoxon signed-rank tests as appropriate. The agreement between pancreatic tumor measurements will be compared among the three institutions using correlation coefficients, percentage agreement, and inter-correlation coefficients.

Quality of life outcomes will be assessed at each time interval and compared using the recommended guidelines from the module. Differences in QOL for the two treatment groups will be explored using a repeated measures model in order to account for the within-patient correlation. Special interest will be placed on exploring the aspects of QOL which are known to be impacted by SBRT.

At this time all research on biomarkers for disease progression is exploratory. The goal is to potentially identify biomarkers that are associated with disease progression. Should any biomarkers be identified, their impact on the time to event outcomes will be summarized using Kaplan Meier curves and they will be tested using Cox proportional hazards models.

Quality of life at each interval will be calculated and compared using the recommended guidelines from the module (available by E-mail: [contact]). Efficacy outcomes with repeated measurements over time (e.g. quality of life) will be analyzed using a generalized estimating equation (GEE) approach to account for within-patient

correlation.

Adverse events will be tabulated by type and grade at each follow-up. All adverse events will be reported to the Data Safety and Monitoring Board (DSMB), GI Clinical Research Groups (CRG) if applicable, and each institution's IRB, as well as to Stanford as the Coordinating Center according to the guidelines set forth in this protocol. The expected toxicity rate is 12% or less and a continuous Bayesian stopping guideline has been developed (see section 17.5.1, p 64) representing the 12% toxicity rate. The study may be stopped before reaching the accrual goal at the recommendation of any of these groups based upon stopping guidelines for toxicity as described below.

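### Section 17.4 names no prognostic covariates for the primary PFS Cox comparison, although usable values are available before randomization

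*Combined protocol and SAP*

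**What the plan says.** The only text that sets the treatment comparison is in Section 17.4 (Plan of Analysis): "Cox proportional hazards models will be used to compare treatment groups and to assess risk factors (e.g. biologic markers and PET volume". No covariate list follows for PFS. Site and leucovorin receipt are each to be tested in Cox models, without saying whether either belongs to the primary model. The same section calls biomarker work exploratory. Section 17.4.1 names ECOG 0-1 versus 2 as a stratifier but does not say how it enters the analysis. Section 17.5.2 bases early stopping on a confidence interval for the HR without naming the model that produces it.

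Two kinds of prognostic information are available before allocation:

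- **CA19-9.** The Study Calendar (Section 14) has the row "Labs: CBCD, CMP, CA19-9 (CEA optional", marked at screening, enrollment and induction. Only CEA is optional in that row.
- **Re-staging CT.** Section 5.2 states "If a patient has radiologically responding or stable disease, s/he may proceed with randomization", and Section 5.3 has sites send the re-staging report to the coordinating center for randomization.

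The examples that Section 17.4 does give are less usable. Research bloods are optional (Section 12.1), and PET is recommended but not required (Section 14).

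**The concern.** In a Cox model, omitting a covariate that predicts outcome makes the treatment test less powerful than an adjusted one, even when the arms are balanced. With 86 patients per arm, an unadjusted estimate also carries any chance imbalance in that covariate. Site and ECOG are the only balancing factors described, so nothing in the allocation balances CA19-9 or tumor size.

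There is also a specification issue. While the model is unnamed, the HR used at the interim and final analyses could be unadjusted, site-adjusted or adjusted for risk factors. A confirmatory trial should close that choice before anyone sees outcomes by arm.

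**Working it through.** **Inputs from Section 17.3.2.**

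- Control median: "the median progression free survival for individuals treated with mFolfinirox alone is estimated to be 6 months".
- Size and target: "A sample size of 172 randomized participants (86 per arm) has 91% power to detect an increase to 10.2 months".
- Distribution: "assuming that the data follows an exponential distribution".
- Timing: "60 months of accrual and a minimum of 12 months of follow-up after randomization".
- Test: "in a 2-sided test with a type 1 error rate of 0.05".
- No dropout rate is given, so none is used.

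**Step 1: reproduce the plan's figure.**

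- HR = 6/10.2 = 0.588.
- With uniform accrual over A = 60 months, F = 12 months and λ = ln 2/median, P(event) = 1 − [exp(−λF) − exp(−λ(A+F))]/(λA). This gives 0.964 for control and 0.893 for SBRT.
- Expected events are 86 × 0.964 = 82.9 and 86 × 0.893 = 76.8, total 159.7. Section 17.5.2 states 83 + 77 = 160.
- Schoenfeld power = Φ(½√160 × |ln 0.588| − 1.96) = Φ(3.356 − 1.96) = 91.9%.
- Freedman power = Φ(√160 × (1 − 0.588)/(1 + 0.588) − 1.96) = Φ(3.28 − 1.96) = 90.6%.

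The stated 91% lies between these two and uses no covariates.

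**Step 2: compare adjusted and unadjusted models.** For each scenario, 4,000 trials were simulated. Each had 172 patients, the same accrual and follow-up, a control median held at 6 months, and one normally distributed prognostic index. A Cox model was fitted with and without the index and tested at two-sided 0.05, ignoring the interim look. The SD of the index on the log-hazard scale is an **assumption**, since the documents give no value. For scale, a median-split factor with HR 2 has SD ½ × ln 2 = 0.35.

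With SD 0, power is 91.1% unadjusted and 91.2% adjusted, so adjusting for an uninformative covariate costs nothing visible.

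| Assumed SD | 0.588 marginal: unadjusted power | 0.588 marginal: adjusted power | 0.588 conditional: unadjusted HR | 0.588 conditional: unadjusted power | 0.588 conditional: adjusted power |
|---|---|---|---|---|---|
| 0.25 | 90.7% | 92.7% | 0.601 | 88.2% | 91.2% |
| 0.50 | 90.0% | 96.2% | 0.631 | 79.7% | 89.5% |
| 0.75 | 89.2% | 98.8% | 0.667 | 68.5% | 88.4% |

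For the marginal columns, the conditional HR was set to 0.575, 0.540 and 0.500, so that the unadjusted Cox model averaged about 0.588 (0.586, 0.588 and 0.587).

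**Step 3: type I error.** With no treatment effect, rejection rates were 5.3% unadjusted and 5.0% adjusted at SD 0.5, and 5.0% and 5.5% at SD 1.0. The Monte Carlo standard error is √(0.05 × 0.95/4000) = 0.34 points, so both models hold the nominal level.

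**Step 4: which reading applies.** Exponential curves in both arms with medians of 6 and 10.2 make 0.588 the arm-level ratio, which favors the marginal reading. The medians alone do not settle it. In the simulation, hazards are constant given the index, so the treated curve is the control curve stretched by 1/HR. The conditional reading therefore also has medians of 6 and 6/0.588 = 10.2, but gives up the exponential shape in each arm. At SD 0.5 the simulated marginal reading has a treated median of 6/0.540 = 11.1. Both readings are reported for that reason.

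**The case against.** A reader might infer that the plan's primary analysis is unadjusted, biased toward no effect and underpowered. The documents do not support that.

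- **The text is silent on adjustment.** Section 17.4 puts the treatment comparison and the risk factors in one sentence without saying whether they share a model. The defect is an unspecified adjustment set.
- **The HR nearer to 1 is not a bias in the test.** Marginal and conditional HRs are different quantities, and the primary objective, median PFS by arm, is a marginal contrast. The error rate of the unadjusted test already allows for chance imbalance.
- **The 91% stands.** On the marginal reading, unadjusted power stays between 89% and 91% for SDs up to 0.75. The low figures arise only on the conditional reading.
- **Prognostic strength is not documented.** No section gives an effect size for CA19-9 or tumor size. Randomizing only stable or responding patients narrows the spread of response. For illustration, if 30% were responders and the HR between responding and stable disease were 1.5, the SD would be ln 1.5 × √(0.3 × 0.7) = 0.19, below the tabulated range.
- **The covariates need definition.** Consent may come before induction or at any time through cycle 4 (Section 4.3), so enrollment CA19-9 is not taken at one common time. Under Study Calendar footnote g, lab records are not required for induction given before enrollment. The eligibility checklist records only a yes/no for stable or better disease, which does not separate responders from stable patients.

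All five points stand. They limit the claim to lost efficiency and an open model choice, and they shape the fix. They do not remove the gain, because adjusted power is higher under both readings at every assumed SD above zero.

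**Conclusion.** The plan forgoes efficiency by prespecifying no prognostic covariates for its primary Cox comparison. The unadjusted test remains valid and the sample-size calculation is correct.

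Over assumed SDs of 0.25 to 0.75, the gain from adjustment is 2.0 to 9.6 points of power if 0.588 is marginal (92.7 − 90.7; 98.8 − 89.2). It is 3.0 to 19.9 points if 0.588 is conditional (91.2 − 88.2; 88.4 − 68.5). A weaker covariate would gain less. The figures assume one normally distributed index, proportional hazards given that index, no dropout and no interim look. They show what could be gained and do not predict this trial's power. The case for change is that some gain is plausible, the cost is small, and the interim and final HR need a named model in any case.

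**What to change.** Before unblinding, name one primary Cox model in the SAP, for use at both the interim and final PFS analyses, containing:

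1. treatment;
2. the allocation factors, ECOG 0-1 versus 2 and site, with the choice between strata and covariates made in advance;
3. log CA19-9, either the protocol-required enrollment value or the last value before randomization, with one chosen and its timing rule stated. The cut-off should be the randomization date, because Section 6.1 also lists CA19-9 before SBRT, and that sample may follow allocation in one arm only;
4. longest tumor diameter on the re-staging scan.

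Set missing baseline values to the mean and add a missingness indicator. Keep leucovorin receipt out of the primary model, since Section 7.1 lets it be decided after randomization. Report the unadjusted HR as supportive.

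The cost is a short SAP paragraph and no new patient procedures. Re-staging diameter has to be extracted from scan reports already submitted, and some CA19-9 values may be missing or differ in timing. The adjusted HR is a conditional estimate and should be labeled so when set beside the arm medians.
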